9.3. Unanticipated Adverse Device Effects (UADE)

An Unanticipated Adverse Device Effect (UADE) is a serious adverse effect on health or safety or any life-threatening problem or death caused by, or associated with, a device, if that effect or problem was not previously identified in nature, severity, or degree of incidence in the investigational plan or application (including a supplementary plan or application), or any other unanticipated serious problem associated with a device that relates to the rights, safety, or

welfare of subjects. Anticipated potential adverse device effects have been identified in the Sponsor Risk Management files.

The Principal Investigator will assure that all unanticipated adverse device effects (UADE) involving risk to subjects or others will be reported to the Sponsor within 24 hours of knowledge of the event. All UADE's will be evaluated and the results of such evaluation will be reported to the IRB within ten (10) working days after the event is reported by the study subjects. The Sponsor will report all SAE's and UADE's to the appropriate regulatory authority. All Serious and Unanticipated Adverse Effects will be reviewed by a Medical Monitor.

10. Device Deficiencies

A device deficiency is an observed or detected inadequacy of an investigational medical device with respect to its identity, quality, durability, reliability, safety or performance/efficacy. Device deficiencies will be collected on the Device Deficiency CRF. Any adverse events resulting from a device deficiency will be collected on the Adverse Event CRF as appropriate.

If the EVA-C System breaks or malfunctions, the device will be returned to the Sponsor and may be replaced with a new device.

Verily will manage the EVA-C System troubleshooting with sites and as well as logistics of device returns and replacement if necessary.

11. Investigational Product(s)/Medical Device

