Description of Study Intervention	Subjects in the intervention arm will undergo a routine clinically-indicated colonoscopy using HD-WLE in conjunction with the EVA-C System. The control group will also undergo a routine clinically-indicated colonoscopy using HD-WLE not aided by the EVA-C System. The EVA-C System is designed to detect polyp-like morphologies. It does not differentiate between adenomatous and hyperplastic polyps. It is up to the colonoscopist's discretion, based on all available information, to decide whether to resect a given polyp, irrespective of the presence of an EVA-C System bounding box. The EVA-C System is not intended to change the colonoscopist's management of an identified lesion.		
Subject Duration	The subject duration is approximately 1-2 hours, including informed consent process and colonoscopy procedure. There is no follow-up required.		
Procedure	Colonoscopy procedure		
	 High Definition White Light Endoscopy will be used, per standard of care. Dye-based or virtual chromoendoscopy may be used for characterizing individual polyps at the colonoscopist's discretion, but may not be used for overall inspection of the colon. Bowel preparation will be evaluated after cleaning and will be scored using the Boston Bowel Preparation Scale (BBPS) separately in each of the three regions of the colon: the right colon (including the cecum and ascending colon), the transverse colon (including the hepatic and splenic flexures), and the left colon (including the descending colon, sigmoid colon, and rectum).¹ Subjects with a BBPS score of 0 or 1 in any of the three colonic regions of the colon will be excluded from the Per Protocol analysis. 		

	 In the right, transverse, and left colon, lesions are to be removed, at the colonoscopist's discretion, per standard of care. Notably, in the left colon, only those lesions that appear adenomatous are to be removed, per standard of care. 				
	In the intervention arm only:				

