9.1. Adverse Events

An Adverse Event (AE) is defined as any untoward medical occurrence, unintended disease or injury in subjects, users or other persons, that is considered a change from baseline or pre-study status, whether or not related to the investigational medical device.

Any pre-existing medical condition or symptoms present in a subject will not be considered an AE in this study, unless it worsens as a result of this study.

For this study, AEs related to the study device and study procedures will be reported on an AE Case Report Form and will include the following: Date/time of onset, date the site first becomes aware of the event, description of the event, the duration of the event, the severity of the event, assessment of the relation of the event to the study device and study procedure, description of action taken, if any, and the event outcome.

In the event medical care to a subject is required, the medical care given to, and medical decisions made on behalf of, subjects should always be the responsibility of a qualified physician.

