9.2. Serious Adverse Events

A Serious Adverse Event (SAE) is defined as an adverse event that is anticipated or unanticipated and which reasonably suggests that one of the manufacturers' devices has or may have caused or contributed to a death or serious injury.

A Serious Adverse Event is an Adverse Event that led to: (a) death, (b) serious deterioration in the health of the subject that either resulted in a (i) life-threatening illness or injury or (ii) permanent impairment of a body structure or a body function, or (iii) in-patient or prolonged hospitalization or (iv) medical or surgical intervention to prevent life-threatening illness or injury or permanent impairment to a body structure or a body function or (c) fetal distress, fetal death or a congenital abnormality or birth defect.

These events are typically reportable to health authorities. For this study, all serious Adverse Events will be reported to the Sponsor within 24 hours of knowledge of the event.

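### Section 9.3 starts the ten-working-day IRB deadline for unanticipated device effects from a subject's report, but the sponsor deadline from knowledge of the event

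*Combined protocol and SAP*

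**What the plan says.** Section 9.3 of the protocol sets two time limits in consecutive sentences. The first makes the Principal Investigator responsible for seeing that UADEs "involving risk to subjects or others" reach the sponsor: each one "will be reported to the Sponsor within 24 hours of knowledge of the event". The second says that every UADE will be evaluated and the results sent to the IRB "within ten (10) working days after the event is reported by the study subjects". It names no role for that submission.

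The same section defines a UADE to include "any life-threatening problem or death caused by, or associated with, a device". Section 9.1 defines an adverse event as reaching beyond subjects: "unintended disease or injury in subjects, users or other persons". It also lists, among the items on the adverse event form, the "date the site first becomes aware of the event". Section 9.2 uses knowledge as the trigger for serious adverse events too: "all serious Adverse Events will be reported to the Sponsor within 24 hours of knowledge of the event".

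The Protocol Summary puts a subject's participation at about 1-2 hours and adds: "There is no follow-up required".

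**The concern.** A reporting deadline needs a start date that exists for every event it governs. The IRB deadline takes its start from something a subject does, although the events include deaths and other serious outcomes that the colonoscopist, study staff or a treating hospital may be first to see. Participation ends within hours and no later contact is required, so a subject report is not something the schedule can be relied on to produce.

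What is at stake is the timeliness of one safety report, and whether anyone can check it. Section 7.2.9 counts adverse events that the investigator fails to report in the protocol's timeframe as a major deviation. Compliance with a deadline that has no start date cannot be monitored in that way. The trial runs at three or more sites and in more than one country, so sites could settle on different readings.

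**Working it through.** The point concerns the start of a reporting period, so there is no planned figure to reproduce. The check is a comparison of the protocol's safety-reporting statements.

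| Report | Limit | What starts it | Where |
|---|---|---|---|
| Serious adverse event to sponsor | 24 hours | Knowledge of the event | Section 9.2 |
| UADE to sponsor | 24 hours | Knowledge of the event | Section 9.3 |
| UADE evaluation to IRB | Ten working days | A report by study subjects | Section 9.3 |
| Serious adverse events and UADEs to regulatory authority | None stated | Not stated | Section 9.3 |
| Medical Monitor review | None stated | Not stated | Section 9.3 |
| Serious adverse events and significant safety findings to IRB/IEC | Set by IRB/IEC procedures | Set by IRB/IEC procedures | Section 12.1 |

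1. **Is the start defined elsewhere?** No. Sections 7.2.8, 9.1, 9.2 and 12.1 give no other start for the ten working days, and the glossary entry for UADE contains no timing.

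2. **Does the trigger fit the events?**
   - Death: if the subject made no report beforehand, there is no start date.
   - Event seen only by staff: no start date unless the subject also reports it.
   - Event affecting a user or another person: that person is not a study subject, so their own report does not meet the literal trigger.

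3. **What happens to the due date?** Call the day the site learns of the event day 0, and suppose the subject reports it d working days later. The sponsor report is due within 24 hours of day 0. As written, the IRB report is due on working day d + 10. With a knowledge trigger it would be due on working day 10. The delay is therefore d working days, and with no subject report there is no due date. The documents give no basis for estimating d.

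4. **Is the duty itself conditional?** No. Section 9.3 requires evaluation and IRB reporting for all UADEs. Only the timing depends on a subject.

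5. **Is a better start date already collected?** Yes. Section 9.1 has the site's awareness date recorded on the adverse event form, but Section 9.3 does not use it.

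**The case against.** The strongest reply is that this is a drafting slip that any site would read sensibly, and that other routes cover the same events. Much of that stands. The sponsor hears within 24 hours of knowledge, a Medical Monitor reviews the event, and the sponsor reports it to the regulatory authority. Section 12.1 separately makes the investigator responsible for notifying the IRB/IEC of serious adverse events and other significant safety findings under IRB/IEC procedures. UADEs are serious by definition and fall within that duty. None of these steps needs a subject report. The study is also classed as non-significant risk.

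Two parts of the reply do not stand. The wording probably is a slip, but nothing in the protocol corrects it, and the plausible intended meanings (reported to the site, reported to the sponsor, known to either) can give different due dates. Section 12.1 states no number of days and does not mention the evaluation results that Section 9.3 promises.

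Two supporting arguments should be used with care. The malfunctions listed in Section 8.3 are poor examples, because effects already identified in the plan in nature, severity and incidence are not UADEs. A malfunction alone is a device deficiency under Section 10. And the consent pages are not available here, so instructions to subjects about reporting problems may exist there.

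**Conclusion.** The two triggers in Section 9.3 are inconsistent, and the IRB trigger does not fit the events it governs. The defect is limited to the start of the ten-working-day period, which is the only IRB limit for UADE evaluations with a stated number of days. It is worth correcting, but it affects no endpoint, sample size or analysis.

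A reader might infer more than the documents support:
- That the clock can never start for a death or an event seen by staff. A subject may also report an event that staff saw, or may report one before it becomes fatal.
- That the IRB would never be told. The duty in Section 9.3 is unconditional, and Section 12.1 provides a separate route.
- That the IRB is the only recipient independent of the sponsor. Section 9.3 also sends UADEs to the regulatory authority.
- That enrolment would go on at every site with no independent body informed. The sponsor and regulatory routes do not wait for a subject, and Section 12.8 lets the sponsor close a site or the study at any time.

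The conclusion rests on a literal reading of Section 9.3 and on the absence of another start date in the supplied text. IRB/IEC procedures, which are not supplied, may set deadlines of their own.

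**What to change.** Reconcile the two sentences in Section 9.3. Start the ten working days from the site's or sponsor's first knowledge of the event, from any source, in line with the trigger used for the 24-hour report. Refer to the site-awareness date on the adverse event form as the recorded start where the site learns first. State which role submits the evaluation results to the IRB, since Section 12.1 assigns IRB notification to the investigator but does not mention the evaluation.

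The cost is about one sentence of protocol text, submitted as an amendment. The site-awareness date is already recorded, so no new data item is needed for it. The downside is that some IRB reports fall due earlier than they would under the present wording.

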11.1. Investigational Product(s)/Device Description

The EVA-C System is a computer-aided detection (CADe) system that uses artificial intelligence to aid in identifying colorectal polyps during High Definition White Light Endoscopy (HD-WLE) based colonoscopies.

CPR, Protocol, Gastroenterology Artificial INtelligence System for detecting **Verily** CPR, Protocol, Gastroenterology Art colorectal polyps (The GAIN Study) Document Number:

Verily CPR, Protocol, Gastroenterology Artificial INtelligence System for detecting colorectal polyps (The GAIN Study)

Document Number:

11.2. **Control Product/Device Description**

This section is not applicable for this study.

11.3. Investigational Device Labeling & Accountability

The Investigator is responsible for accountability at the study site. The Investigator should take adequate precautions, including storage of the investigational study devices to prevent diversion of the products into unauthorized channels of distribution. All unused products will be returned to the Sponsor.

The EVA-C System is an investigational device and will be packaged with a label with the name and place of business of the manufacturer and distributor. The device will also be labeled with the following: "CAUTION: Investigational device. Limited by Federal (or United States) law to investigational use." Devices used outside the United States will be labeled with the following: "CAUTION: Investigational device. For use in clinical studies only."

The investigational device label information will be transcribed to the appropriate case report form as well as for device accountability and traceability.

Only sites/Investigators participating in the clinical study will be eligible to receive the EVA-C System after Verily has declared the site ready to start the clinical study.

At the end of the study, all investigational devices must be returned to the Sponsor. To return the devices to Verily, a Return Material Authorization (RMA) number is required. The site will contact Verily to issue an RMA number, and Verily will provide the site with appropriate device return packaging and shipment materials. The Sponsor-issued RMA number will be captured within the appropriate shipping and/or device accountability documentation.

12. Regulatory, Ethical and Study Oversight Considerations

12.1. Regulatory and Ethical Considerations

This study will be conducted in accordance with the protocol and with the following:

- Consensus ethical principles derived from international guidelines including the Declaration of Helsinki and Council for International Organizations of Medical Sciences (CIOMS) International Ethical Guidelines
- Applicable ICH Good Clinical Practice (GCP) Guidelines
- Applicable laws and regulations

The protocol, protocol amendments, ICF, IB, and other relevant documents (eg, advertisements) must be submitted to an IRB/IEC by the investigator and reviewed and approved by the IRB/IEC before the study is initiated.

Any amendments to the protocol will require IRB/IEC approval before implementation of changes made to the study design, except for changes necessary to eliminate an immediate hazard to study subjects.

The investigator will be responsible for the following:

- Providing written summaries of the status of the study to the IRB/IEC annually or more frequently in accordance with the requirements, policies, and procedures established by the IRB/IEC
- Notifying the IRB/IEC of SAEs or other significant safety findings as required by IRB/IEC • procedures; and

 Providing oversight of the conduct of the study at the site and adherence to requirements of 21 CFR, ICH guidelines, the IRB/IEC, European regulation 536/2014 for clinical studies (if applicable), and all other applicable local regulations

12.2. Financial Disclosure

Investigators and sub-investigators will provide the sponsor with sufficient, accurate financial information as requested to allow the sponsor to submit complete and accurate financial certification or disclosure statements to the appropriate regulatory authorities. Investigators are responsible for providing information on financial interests during the course of the study and for 1 year after completion of the study.

12.3. Informed Consent Process

Subjects must be given ample time and opportunity to inquire about details of the study and to decide whether or not to participate in the study before informed consent is obtained and per sites' local and IRB guidelines. The investigator or his/her representative will explain the nature of the study to the subject and answer all questions regarding the study.

Subjects must be informed that their participation is voluntary. Subjects will be required to sign a statement of informed consent that meets the requirements of 21 CFR 50, local regulations, ICH guidelines, Health Insurance Portability and Accountability Act (HIPAA) requirements, where applicable, and the IRB/IEC or study center.

There must be a source document that includes a statement that written informed consent was obtained before the subject was enrolled in the study and the date the written consent was obtained. The authorized person obtaining the informed consent must also sign the ICF.

Subjects must be re-consented to the most current version of the ICF(s) during their participation in the study.

A copy of the ICF(s) must be provided to the subject or the subject's legally authorized representative.

12.4. Data Protection

Subjects will be assigned a unique identifier by the sponsor. Any subject records or datasets that are transferred to the sponsor will contain the identifier only; subject names or any information which would make the subject identifiable will not be transferred.

The subject must be informed that his/her personal study-related data will be used by the sponsor in accordance with local data protection laws. The level of disclosure must also be explained to the subject. All data used in the analysis and reporting of this evaluation will be used in a manner without identifiable reference to the study subject.

The subject must be informed that his/her medical records may be examined by Clinical Quality Assurance auditors or other authorized personnel appointed by the sponsor, by appropriate IRB/IEC members, and by inspectors from regulatory authorities.

12.5. Interim Analysis Structure

An independent statistician will be utilized for the interim analysis. Within Verily and/or a designee, data and programming for the interim analysis will be performed by an interim analysis dedicated group who are not involved in the management of the study. This group will

communicate with the independent statistician and will provide the unblinding codes. The independent statistician will execute the unblinding with the set of programs prepared by the interim analysis dedicated group and will then communicate the results to a pre-selected group within Verily not involved in the management of the study. A detailed unblinding and a communication plan will be provided in the statistical analysis plan.

12.6. Data Quality Assurance

- All subject data relating to the study will be recorded on printed or electronic CRF unless transmitted to the sponsor or designee electronically (eg, laboratory data). The investigator is responsible for verifying that data entries are accurate and correct by physically or electronically signing the CRF.
- The investigator must maintain accurate documentation (source data) that supports the information entered in the CRF.
- The investigator must permit study-related monitoring, audits, IRB/IEC review, and regulatory agency inspections and provide direct access to source data documents.
- Monitoring details describing strategy (eg, risk-based initiatives in operations and quality such as Risk Management and Mitigation Strategies and Analytical Risk-Based Monitoring), methods, responsibilities and requirements, including handling of noncompliance issues and monitoring techniques (central, remote, or on-site monitoring) are provided in the Monitoring Plan.
- The sponsor or designee is responsible for the data management of this study including quality checking of the data.
- The sponsor assumes accountability for actions delegated to other individuals (eg, Contract Research Organizations).
- Study monitors will perform ongoing source data verification to confirm that data entered into the CRF by authorized site personnel are accurate, complete, and verifiable from source documents; that the safety and rights of subjects are being protected; and that the study is being conducted in accordance with the currently approved protocol and any other study agreements, ICH GCP, and all applicable regulatory requirements.
- Records and documents, including signed ICFs, pertaining to the conduct of this study must be retained by the investigator for 2 years after study completion unless local regulations or institutional policies require a longer retention period. No records may be destroyed during the retention period without the written approval of the sponsor. No records may be transferred to another location or party without written notification to the sponsor.

12.7. Source Documents

- Source documents provide evidence for the existence of the subject and substantiate the integrity of the data collected. Source documents are filed at the investigator's site.
- Data reported on the CRF or entered in the eCRF that are transcribed from source documents must be consistent with the source documents or the discrepancies must be explained. The investigator may need to request previous medical records or transfer records, depending on the study. Also, current medical records must be available.
- If study data is recorded directly on the CRFs (i.e., no prior written or electronic record of data), it is considered to be source data.
- Definition of what constitutes source data can be found in CRF completion guidelines.

12.8. Study and Site Closure

The sponsor designee reserves the right to close the study site or terminate the study at any time for any reason at the sole discretion of the sponsor. Study sites will be closed upon study completion. A study site is considered closed when all required documents and study supplies have been collected and a study-site closure visit has been performed.

The investigator may initiate study-site closure at any time, provided there is reasonable cause and sufficient notice is given in advance of the intended termination.

Reasons for the early closure of a study site by the sponsor or investigator may include but are not limited to:

- Failure of the investigator to comply with the protocol, the requirements of the IRB/IEC or local health authorities, the sponsor's procedures, or GCP guidelines
- Inadequate recruitment of subjects by the investigator
- Discontinuation of further study intervention development

